RO-APM	Radiation Oncology-Alternative Payment Model
ROSAC	Radiation Oncology Safety Assurance Committee
RT	Radiation Therapy
SAE	Serious Adverse Event
SCCC	Simmons Comprehensive Cancer Center
SD	Stable Disease
UPIRSO	Unanticipated Problems Involving Risks to Subjects or Others
UTSW	University of Texas Southwestern Medical Center
UW-QOL	University of Washington Quality of Life Questionnaire
VMAT	Volumetric Modulated Arc Therapy

STUDY SCHEMA

STUDY SUMMARY

Title	HYHOPE: Phase I study of de-intensified hypofractionated radiation therapy for human papilloma virus-associated oropharynx cancer
Short Title	HYHOPE: De-intensified hypofractionated radiation therapy for HPV-associated oropharynx cancer
Protocol Number	STU 2020-1079
Phase	Phase I
Methodology	Rolling 6 dose finding cohort followed by dose expansion cohort
Study Duration	3 years to accrue, additional 1 year of follow-up
Study Center(s)	Single-center
Objectives	To assess the maximum tolerated dose/fractionation and signal for efficacy of de-intensified hypofractionated radiotherapy for favorable HPV-associated oropharynx cancer
Number of Subjects	24
Diagnosis and Main Inclusion Criteria	T1-3 (≤ 6 cm), N0-2 (except T1-2N0) p16 positive oropharyngeal squamous cell carcinoma with ≤ 10 pack-year smoking history
Study Product(s), Dose, Route, Regimen	Hypofractionated intensity modulated radiotherapy with concurrent chemotherapy (weekly cisplatin)
Duration of administration	3-4 weeks
Reference therapy	Conventionally fractionated radiotherapy (60-70 Gy) over 6-7 weeks with concurrent chemotherapy (historical control)
Statistical Methodology	Phase I: standard rolling 6 design to determine the maximum tolerated dose/fractionation. Additional patients will be enrolled to reach 24 patients to achieve 20 evaluable patients for the clinical response endpoint assuming a 15% attrition rate.

1.0 BACKGROUND AND RATIONALE

1.1 Disease Background

The incidence of Human Papilloma Virus-associated oropharyngeal squamous cell carcinoma (HPVOPSCC) is increasing in the United States accounting for 70-80% of newly-diagnosed oropharyngeal cancers. With the recognition of HPVOPSCC as a distinct disease process from the smoking- or alcohol-related head and neck cancers and the associated favorable prognosis (1), investigations are ongoing to determine the best strategy to de-intensify therapy while maintaining good oncologic outcomes. Recently published results of reduced dose radiotherapy (RT) of 60 Gy with weekly cisplatin (30 mg/m²) have shown excellent outcomes with 2- and 3-year progression free survival (PFS) of 86% and 85%, respectively, and 2- and 3-year overall survival (OS) of 95% (2). Preliminary results of NRG-HN002 was also recently presented at ASTRO 2019 with 2-year PFS of 90.5% in the 60 Gy RT plus weekly cisplatin (40 mg/m²) arm while surpassing the pre-specified MD Anderson Dysphagia Inventory scale threshold (3). Although we do not have randomized data compared to the current standard of 70 Gy, 60 Gy with concurrent weekly chemotherapy is likely to become an important treatment strategy for favorable HPVOPSCC, perhaps representing the purest de-intensification paradigm without the addition of upfront surgery or induction chemotherapy.

1.2 Study Agent(s)/Therapy(ies) Background and Associated Known Toxicities

Standard of care RT for head and neck squamous cell carcinoma (HNSCC) involves conventionally fractionated treatment of 2 Gy per fraction delivered over a course of 6-7 weeks, representing one of the longest RT courses among all cancers. In other disease sites including breast and prostate, moderately hypofractionated RT (HFRT) has been demonstrated to provide equivalent oncologic outcomes with similar toxicities (4, 5). However, concerns for potential increase in side effects have limited attempts of HFRT in HNSCC except in early stage glottic larynx cancer where treatment volumes are relatively small. In this disease subsite, moderately HFRT delivered in 2.25 Gy per fraction were shown to have superior local control with no significant increase in adverse reactions (6).

A small number of prospective trials using moderately HFRT in other HNSCC subsites have been reported. In a study of definitive chemoradiation delivering 55 Gy in 20 fractions (2.75 Gy/fraction) with concurrent carboplatin in 19 patients with HNSCC, all patients were able to complete RT with a complete response rate of 84% and 2-year local control of 75% (7). Acute grade 3 dermatitis and mucositis were seen in 26% and 84% of patients, respectively. In another small single arm trial, 20 patients were treated with 55 Gy in 20 fractions with concurrent weekly cisplatin (8). All patients were able to complete RT as prescribed with acute grade 3 dermatitis, grade 3 mucositis, and nasogastric tube rate of 30%, 40%, and 75%, respectively. Although the acute adverse reaction appeared to be comparable to conventionally fractionated RT, neither trial reported long term complication rates.

There are currently two ongoing multicenter randomized trials outside of the United States randomizing patients to HFRT vs conventionally fractionated RT in the definitive setting. In a trial sponsored by the International Atomic Energy Agency (IAEA-HYPNO), patients with stage I-IV HNSCC are being randomized to 55 Gy in 20 fractions 5 times a week vs 66 Gy in 33 fractions six times a week with primary endpoints of 3-year locoregional control and late toxicity. In another trial from the United Kingdom (COMPARE), patients with intermediate and high risk oropharyngeal cancers are being randomized to four different arms, two of which involve 64 Gy in 25 fractions (2.56 Gy/fraction) vs 70 Gy in 35 fractions with the primary endpoint of overall survival. Both trials are scheduled to complete accrual in 2021 with results likely reported in mid- to late-

2020s. There are no published or active trials assessing curative HFRT regimen with less than 20 fractions.

Study of HFRT is of particular interest as the health care system transitions to value-based care model. A change in the reimbursement model for radiation oncology in the United States will likely significantly affect the way RT is delivered in the near future. Centers for Medicare and Medicaid Services (CMS) have recently unveiled the radiation oncology alternative payment model (RO-APM), which is scheduled to take effect between now and 2022. Participation will be mandatory, and radiation oncology centers will receive a fixed payment for a 90-day episode of care in contrast to the current fee-for-service model where each visit and fraction is billed for and reimbursed (9). RO-APM is designed to incentivize cost-effective treatments while maintaining high quality. As a result of this change, the radiation oncology community will seek safe and effective strategies to decrease total costs per episode. A prospective study to assess HFRT with fewer number of fractions is thus timely and potentially paradigm changing for practices across the United States.

The current COVID-19 pandemic is highlighting the cost and risk to our society at large of a lack of viable alternatives to a 6-7 week daily RT course for patients with HNSCC. Patients and medical staff are exposed to increased risk of SARS-CoV-2 infection during a prolonged daily RT course. A well-validated HFRT regimen for HNSCC is urgently needed similar to other disease sites such as breast, prostate, rectum, and brain where safe and effective HFRT regimens have been established and are increasingly utilized.

1.3 Other Agents

The standard concurrent chemotherapy for the treatment of HNSCC consists of bolus cisplatin (100 mg/m^2) every 3 weeks for 2-3 cycles, which is associated with significant grade 3-4 toxicity (10, 11). As noted above, multi-institutional and national trials assessing low dose weekly cisplatin ($30-40 \text{ mg/m}^2$) with RT for favorable HPVOPSCC have shown excellent oncologic results with a favorable toxicity profile (2, 3). The current trial will test HFRT with concurrent weekly cisplatin at 40 mg/m^2 .

1.4 Rationale

1.4.1 Dose de-intensification

Analysis of multiple prospective trials have confirmed improved PFS and OS of patients with HPVOPSCC vs non-HPV associated cancers (12-14). Given the significant toxicity associated with standard chemoradiation of 70 Gy with concurrent cisplatin, it is imperative to identify optimal strategies to de-intensify therapy for favorable HPVOPSCC to achieve comparable outcomes to standard therapy while minimizing toxicity. Several Phase II studies have shown promising results using 60 Gy vs the current standard of 70 Gy (2, 3).

1.4.2 Volume de-escalation

Elective nodal volumes for head and neck cancer currently used for intensity-modulated RT (IMRT) is extrapolated from conventional RT fields. Assessment of patterns of failure following IMRT treatments have shown that regional recurrences almost always occur in the high-dose region and solitary failure in the elective volume/dose is rare (15-18). Trials assessing a reduction in the elective nodal volume following induction chemotherapy have shown no solitary elective volume failures (19, 20). More recently, a UT Southwestern Medical Center prospective study of volume de-escalation, where patients with oropharynx cancer received elective dose RT only to the involved and immediately adjacent cervical nodal levels, found no solitary nodal recurrences in

the treated or untreated elective neck volumes, with a minimum follow-up of nearly 2 years (21). Decreasing the volume of elective treatment can improve the toxicity profile of treatment and is currently being incorporated into the standard-of-care arm in large cooperative group trials such as NRG-HN005.

1.4.3 **Hypofractionation**

Cost of oncologic care has continued to increase with efforts in recent years to transition to a value-based care model. In this environment, especially with the implementation of the RO-APM described above, there is an economic rationale to elucidate ways to provide quality care while decreasing resource utilization. Also, there is a strong radiobiological rationale for HFRT in HNSCC to decrease the overall treatment time and thus minimize the effects of accelerated repopulation seen in this disease entity. Accelerated fractionation with its associated decrease in overall treatment time has been shown to improve local control and progression free survival compared to conventional fractionation in HNSCC (22). Effective and safe radiation treatment in a fraction of the time currently required will also improve patient quality of life by decreasing interruptions to their personal and professional lives. Moreover, reducing the overall treatment time may increase completion rates and compliance by reducing the time burden of the therapy. Shortened treatment time will lead to reduced number of weekly cisplatin cycles with concomitant decrease in total cumulative dose, which may also decrease potential chemotherapy side effects such as ototoxicity or nephrotoxicity.

2.0 STUDY OBJECTIVES

2.1 Primary Objectives

2.1.1 To determine the maximally tolerated dose/fractionation (MTD) of HFRT

2.2 Secondary Objectives

2.2.1 To assess physician-reported acute and late toxicities of HFRT

2.2.2 To assess the oncologic outcomes of HFRT

2.2.3 To assess patient-reported QOL of HFRT

2.2.4 To assess feeding tube dependence rate of HFRT

2.3 Endpoints

2.3.1 Primary endpoint: MTD of HFRT

2.3.2 Secondary endpoints:

- Physician-reported acute and late toxicities
 - Rate of \geq grade 3 acute toxicities during treatment, and at 1 and 3 months after treatment using National Cancer Institute (NCI) Common Terminology Criteria for Adverse Events (CTCAE) version 5.0
 - Rate of \geq grade 3 late toxicities at 6 and 12 months after treatment using CTCAE v5.0
- Oncologic outcomes: locoregional control (LRC), progression-free survival (PFS), and overall survival (OS)

- Patient-reported QOL:
 - MDADI, University of Washington QOL questionnaire (UW-QOL) version 4, and EuroQol-5 dimensions (EQ-5D-5L) scores at baseline, 1, 3, 6, and 12 months after treatment. QOLs will be completed either on paper (included in Appendix C, D & E of the protocol) or electronically via MyChart.
- Feeding tube dependence rate at baseline, 1, 3, 6, and 12 months after treatment
 - Feeding tube dependence defined as daily use of the feeding tube with ≥ 2 nutritional supplements (e.g. Ensure, Boost, etc.) per day at the time of consultation.

3.0 SUBJECT ELIGIBILITY

Eligibility waivers are not recommended; however, if warranted, prior approvals are required per section 10.5.1. Subjects must meet all inclusion and exclusion criteria to be registered to the study. Study treatment may not begin until a subject is registered. Once registered, a subject is still required to meet all inclusion and exclusion criteria on the first day of treatment, prior to treatment.

3.1 Inclusion Criteria

- 3.1.1 Pathologically-proven diagnosis of T1-3 (up to 6 cm), N0-2 (AJCC 8th edition) p16 positive squamous cell carcinoma of the oropharynx (except T1-2N0 as noted in the exclusion criteria)
- 3.1.2 ≤ 10 pack-year smoking history and not actively smoking
- 3.1.3 Age ≥ 18 years
- 3.1.4 ECOG performance status 0-2 or Karnofsky Performance Status of 50-100
- 3.1.5 Women of child-bearing potential and men must agree to use adequate contraception (hormonal or barrier method of birth control; abstinence) prior to study entry, for the duration of study participation, and for 90 days following completion of therapy. Should a woman become pregnant or suspect she is pregnant while participating in this study, she should inform her treating physician immediately.
 - 3.1.5.1 A female of child-bearing potential is any woman (regardless of sexual orientation, marital status, having undergone a tubal ligation, or remaining celibate by choice) who meets the following criteria:
 - Has not undergone a hysterectomy or bilateral oophorectomy; or
 - Has not been naturally postmenopausal for at least 12 consecutive months (i.e., has had menses at any time in the preceding 12 consecutive months).
- 3.1.6 Negative serum or urine pregnancy test within 2 weeks before registration for women of childbearing potential.
- 3.1.7 Ability to understand and the willingness to sign a written informed consent.

3.2 Exclusion Criteria

- 3.2.1 Distant metastasis
- 3.2.2 T1-2N0 (AJCC 8th edition) p16 positive squamous cell carcinoma of the oropharynx (candidates for definitive RT alone or surgery alone)
- 3.2.3 Inability to receive concurrent weekly cisplatin due to comorbid conditions
- 3.2.4 Synchronous non-skin cancer primaries outside of the oropharynx, oral cavity, larynx, and hypopharynx except for low- and intermediate-risk prostate cancer and well-differentiated thyroid cancer. For prostate cancer, patient should not be receiving active treatment. For thyroid cancer, thyroid surgery may occur before or after radiation treatment, provided all other eligibility criteria are met.
- 3.2.5 Prior invasive malignancy with an expected disease-free interval of less than 3 years
- 3.2.6 Prior radiotherapy to the region of the study cancer that would result in overlap of radiation fields
- 3.2.7 Subjects may not be receiving any other investigational agents for the treatment of the cancer under study.
- 3.2.8 History of allergic reactions attributed to compounds of similar chemical or biologic composition to the chemotherapy agents in this study
- 3.2.9 Uncontrolled intercurrent illness including, but not limited to, ongoing or active infection, symptomatic congestive heart failure, unstable angina pectoris, cardiac arrhythmia, or psychiatric illness/social situations that, in the opinion of the investigator, would limit compliance with study requirements
- 3.2.10 Subjects must not be pregnant or nursing due to the potential for congenital abnormalities and the potential of this regimen to harm nursing infants.
- 3.2.11 History of severe immunosuppression, including HIV, organ or autologous or allogeneic stem cell transplant, or active immunosuppressive medication at the time of enrollment

4.0 TREATMENT PLAN

4.1 Radiation Treatment Dose and Administration

Patients will be enrolled on the trial in cohorts of up to 6 per the rolling 6 dose escalation design as outlined in section 9.1.1.

4.1.1 CT simulation

Patients will be simulated supine in a thermoplastic mask extending from the scalp through upper chest (e.g. “5 point mask”) or a thermoplastic mask covering the head in combination with shoulder retractors. IV contrast is recommended but not mandatory.

4.1.2 Dose and fractionation

Dose calculation for HFRT was based on the biologically effective dose (BED) model accounting for time/repopulation observed in HNSCC:

$$BED = n(d/[\alpha/\beta]) - \log_2(T - Tk)/\alpha T p$$

n = number of fractions

d = dose per fraction

T = overall treatment time

Conventionally fractionated RT: 40 days (30 fractions)

Hypofractionated RT: 19 days (12-15 fractions), 26 days (20 fractions)

Tk = time delay of repopulation (21 days for tumor, 7 days for mucosa)

Tp = cell doubling time (3 days for tumor, 2.5 days for mucosa)

$\alpha/\beta = 3$ for late complications, 10 for tumor/mucosa

$\alpha = 0.35 \text{ Gy}^{-1}$

Dose and fractionation were selected to satisfy two parameters (see Table):

- $\leq \text{BED}_3$ vs conventional fractionation (60 Gy), i.e. late toxicity dose to normal tissue
- $\geq \text{BED}_{10}$ vs conventional fractionation (60 Gy), i.e. dose to tumor

Table. Total dose BED calculation for HFRT (vs comparison [conventional fractionation])

Level	Dose	BED /w repopulation $\alpha/\beta = 10$ (tumor)	BED /w repopulation $\alpha/\beta = 10$ (acute mucosa)	BED $\alpha/\beta = 3$ (late normal tissue)
1*	44.4 Gy/12 fx (3.7 Gy/fx), 4 fx/week	64	52	99
0	46.5 Gy/15 fx (3.1 Gy/fx), 5 fx/week	61	51	95
-1	52 Gy/20 fx (2.6 Gy/fx), 5 fx/week	62	50	97
Comparison	60 Gy/30 fx (2 Gy/fx), 5 fx/week	59	46	100

Abbreviations: fx, fraction(s)

*Level 1 eliminated at time of amendment. See the end of the section for details.

Level 0 will test a 15-fraction HFRT regimen treated 5 times a week for 3 weeks. If successful, level 1 will test a 12-fraction HFRT regimen treated 4 times a week for 3 weeks. If level 1 is well-tolerated, this regimen will be considered maximally tolerated dose/fractionation (i.e. no further reduction in the number of fractions).

If Level 0 is deemed intolerable, patients will be enrolled on level -1, which will test a 20-fraction HFRT regimen treated 5 times a week for 4 weeks. Given published literature on 20-fraction regimens, we anticipate that a 20-fraction regimen will be tolerable.

The calculated BED for acute toxicity such as the normal mucosa may be slightly increased vs conventionally fractionated RT, but the dose ranges **are well below** the limits deemed tolerable (<59-63 Gy₁₀) based on analysis of toxicities associated with various head and neck cancer fractionation regimens published to date (23).

High risk (HR: regions of positive disease) and standard risk (SR: other regions at risk) volumes will receive doses as outlined below using dose painting intensity-modulated radiotherapy (IMRT):

Level 1:

- PTVHR: $370 \text{ cGy} \times 12 = 4440 \text{ cGy}$
- PTVSR: $330 \text{ cGy} \times 12 = 3960 \text{ cGy}$

Level 0:

- PTVHR: $310 \text{ cGy} \times 15 = 4650 \text{ cGy}$
- PTVSR: $270 \text{ cGy} \times 15 = 4050 \text{ cGy}$

Level -1:

- PTVHR: $260 \text{ cGy} \times 20 = 5200 \text{ cGy}$
- PTVSR: $230 \text{ cGy} \times 20 = 4600 \text{ cGy}$

Table. Standard risk dose BED calculation for HFRT (vs comparison)

Level	Dose	BED /w repopulation $\alpha/\beta = 10$ (tumor)	BED /w repopulation $\alpha/\beta = 10$ (acute mucosa)	BED $\alpha/\beta = 3$ (late normal tissue)
1*	39.6 Gy/12 fx (3.3 Gy/fx)	53	43	83
0	40.5 Gy/15 fx (2.7 Gy/fx)	51	42	77
-1	46 Gy/20 fx (2.3 Gy/fx)	53	41	81
Comparison	54 Gy/30 fx (1.8 Gy/fx)	51	37	86

Abbreviations: fx, fraction(s)

*Level 1 eliminated at time of amendment. See the end of the section for details.

Elimination of Level 1

Upon a preliminary review of the toxicity profile of patients enrolled on a parallel Phase I trial in the post-operative setting with the same fractionation scheme, an apparent increase in acute grade 2 and grade 3 toxicities related to oral/pharyngeal mucositis and pain was observed on dose level 1 vs level 0. Although dose limiting toxicity is not expected at the conclusion of the evaluation period for patients on level 1 on that trial, the investigators have made a decision to forgo escalation to level 1 (i.e. eliminate level 1) for this current trial in light of potential increase in toxicity. As delineated in the tables above, the fractionation schemes of level 0 and 1 have the same biologically effective dose to the tumor and treatment length (3 weeks). The trial will proceed with the dose expansion phase once level 0 is confirmed to be without dose limiting toxicities.

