7.5 Stopping Rules

The primary hypothesis of the phase 1 study is that de-intensified HFRT is safe and tolerable. The trial will terminate during the rolling 6 dose escalation phase if it has reached level -1 and 2 patients experience dose limiting toxicity (DLT) at this dose level.

The secondary hypothesis is that the crude 1-year LRC rate is at least 85% (based on historical controls). In other words, for the target of 20 evaluable patients at 1 year, up to 3

patients can have a LRR and satisfy the pre-specified hypothesis. Thus, if a 4th patient enrolled on the trial experiences LRR within 1 year of completing the study treatment, the trial will be terminated for futility.

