8.1.1 Return and Retention of Study Drug Not applicable

9.0 STATISTICAL CONSIDERATIONS

9.1 Study Design/Study Endpoints

9.1.1 Study design:

Phase I Rolling 6 design with dose expansion cohort
 Study design will be a rolling 6 dose escalation study, a modification to the standard 3 + 3 design (29). In contrast to the 3 + 3 design where patients are enrolled in cohorts of 3, the rolling 6 design allows for continuous enrollment up to a total of 6 patients at the same dose level. The dose level assigned to a new patient is based on the number of patients currently enrolled and evaluable, and the number of patients experiencing a DLT. Once six patients have been enrolled at the current dose level, enrollment will stop until at least 5 of the 6 patients have completed evaluation for DLT. Escalation to the next dose level occurs if at time of enrollment 3/3, 4/4, 5/5, 5/6, or 6/6 patients at the dose level are evaluated for and without DLT. De-escalation occurs if at the time of enrollment, 2 or more patients have experienced a DLT at the dose level.

DLT definition:

- Any CTCAE grade 4 toxicity (generally described as life-threatening consequences with urgent intervention indicated) attributed to RT during and up to 3 months post-treatment
- Persistent CTCAE grade 3 mucositis at 3 months post-treatment
 - CTCAE definitions:
 - Oral mucositis: severe pain; interfering with oral intake
 - Pharyngeal mucositis: severe pain; unable to adequately aliment or hydrate orally; limiting self-care ADL
 - To decrease subjectivity of interpretation by each clinician, the definition for grade 3 mucositis was consolidated as below:
 - Severe pain defined as needing daily opioid use of >30 morphine equivalent dose during the past week for mucositis, AND
 - The pain interferes with oral intake or swallowing defined as tolerating a liquid only diet or requiring tube feeds (with the exception of patients who were on a liquid only diet at baseline prior to RT, in which case they would need to be feeding tube dependent to satisfy this definition).

MTD definition: highest dose/fractionation level among those listed in section 4.1.2 at which ≤ 1 of 6 patients have experienced a DLT.

During the dose expansion phase, patients will be enrolled at MTD to reach the total accrual goal of 24 patients.

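### Release of level 0 for expansion has two thresholds: literally zero DLTs in 4.1.2, at most one DLT in six in 9.1.1

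*Combined protocol and SAP*

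**What the plan says.** The paragraph on the elimination of Level 1, at the end of section 4.1.2, is current text and sets the condition for moving on: "The trial will proceed with the dose expansion phase once level 0 is confirmed to be without dose limiting toxicities". It gives no number of patients. Earlier in 4.1.2, the route downwards is worded as: "If Level 0 is deemed intolerable, patients will be enrolled on level -1". No number is attached to that either.

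Section 9.1.1 gives the numeric rules. The MTD is the highest listed level "at which ≤ 1 of 6 patients have experienced a DLT". On expansion it says: "During the dose expansion phase, patients will be enrolled at MTD to reach the total accrual goal of 24 patients". On moving down: "De-escalation occurs if at the time of enrollment, 2 or more patients have experienced a DLT at the dose level". On moving up: "Escalation to the next dose level occurs if at time of enrollment 3/3, 4/4, 5/5, 5/6, or 6/6 patients at the dose level" have been evaluated and are free of DLT. Section 7.5 stops the trial in dose finding "if it has reached level -1 and 2 patients experience dose limiting toxicity (DLT) at this dose level".

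Two cross-references bear on which text governs. Section 4.1 enrols patients "per the rolling 6 dose escalation design as outlined in section 9.1.1", and 9.3.1.1 likewise refers to 9.1.1 for determining the MTD.

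**The concern.** The MTD is the sole primary endpoint, and with Level 1 gone the main dose decision left is whether level 0 (15 fractions) is released for expansion. Two current sections state that release condition differently. If one of six patients has a DLT, 9.1.1 makes level 0 the MTD and opens expansion there, while 4.1.2 taken at its word does not open it. The team would have to settle which text applies during the trial, knowing that a DLT had occurred. A pre-specified rule is meant to prevent exactly that.

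The context of the 4.1.2 sentence adds to the doubt. It was written when the investigators gave up Level 1 because of increased grade 2 and 3 mucositis and pain in a parallel trial. A stricter gate is a possible intention, and the text does not tell the reader whether it was meant.

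**Working it through.** **The plan's own figure.** Section 9.2 wants 20 evaluable patients at 1 year with 15% attrition: 20 / (1 − 0.15) = 23.5, rounded up to 24. This reproduces, and nothing below changes it.

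**The two rules side by side, for six evaluated patients at level 0**

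| DLTs in six | Section 9.1.1 | Section 4.1.2, read literally |
|---|---|---|
| 0 | Level 0 meets the MTD definition; expand | Expand |
| 1 | Level 0 meets the MTD definition (≤ 1 of 6); 5/6 is a pass; de-escalation not triggered; expand | Release condition not met; no action stated |
| 2 or more | De-escalate to level -1 | Release condition not met; level -1 if deemed intolerable |

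The sections differ in substance only in the middle row. Section 7.5 does not settle it, because its DLT limit applies to level -1 only. That limit also tolerates one DLT, as 9.1.1 does.

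**How likely the middle row is.** The documents give no true DLT rate, so p is an assumption. With six patients and q = 1 − p:

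- zero of six: q^6
- exactly one of six: 6 × p × q^5
- at most one of six: the sum of the two

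At p = 5%: q^6 = 0.95^6 = 0.735; 6 × 0.05 × 0.95^5 = 0.232; sum 0.967.

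| Assumed p | Exactly 1 of 6 (sections differ) | Released under zero of six | Released under ≤ 1 of 6 |
|---|---|---|---|
| 2% | 10.8% | 88.6% | 99.4% |
| 5% | 23.2% | 73.5% | 96.7% |
| 10% | 35.4% | 53.1% | 88.6% |
| 20% | 39.3% | 26.2% | 65.5% |

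**Which rows are plausible.** A DLT under 9.1.1 is a grade 4 toxicity attributed to RT up to 3 months after treatment, or grade 3 mucositis still present at 3 months under a tightened definition. That is narrow. Section 4.1.2 also reports that no DLT was expected even at Level 1 of the parallel trial. That trial is in the post-operative setting, so it is only indirect evidence, but it points the same way. I would give weight to the 2% to 10% rows. The 20% row only shows how the result behaves at a higher rate.

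**The case against.** The strongest reply is that the 4.1.2 sentence is shorthand. It closes a narrative paragraph on why Level 1 was dropped and contains no count and no de-escalation action. In the pass rule of 9.1.1, being free of DLT describes the patients who pass, and 5/6 is a pass. On that reading 4.1.2 simply means that level 0 has passed 9.1.1. The cross-references in 4.1 and 9.3.1.1 support this. Most of this stands: 9.1.1 is the better candidate for the governing text. But neither cross-reference defines or overrides the release condition in 4.1.2, and 4.1.2 does not itself point to 9.1.1 for it.

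Three stronger readings are tempting, and the documents do not support them.

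- A reader might infer that one DLT in six leaves the trial with no next step. Section 9.1.1 alone supplies one: level 0 is the MTD, and expansion proceeds there.
- A reader might infer that one DLT could send patients to the 20-fraction level. That would contradict the rule in 9.1.1 that de-escalation takes two or more.
- A reader might infer from the surviving 3/3, 4/4 and 5/5 wording that expansion could open after three clean patients. The MTD definition is framed on six. At the stated 3 patients per month, and a DLT window of about 110 days (assumed: 19 days of RT plus about 3 months, or 3.6 months), about 3 × 3.6 = 10.8 patients would present before the first was fully evaluated. The cohort would in practice be full.

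**Conclusion.** The point holds as an inconsistency left by the amendment. Two current sections state different release thresholds for level 0, and they conflict at exactly one DLT in six. The probability of that outcome is about 11%, 23% and 35% at assumed true DLT rates of 2%, 5% and 10%, with the lower end more plausible. These figures rest on six evaluable patients with independent outcomes and on rates that the documents do not supply.

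The realistic consequence is an avoidable judgement call on the primary endpoint during the trial. A wrong MTD is not the expected result, since the weight of the text favours ≤ 1 of 6. It should be corrected because it concerns the only primary endpoint and the correction is short.

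**What to change.** - In 4.1.2, replace the release phrase with: once level 0 meets the MTD definition in 9.1.1 (≤ 1 DLT in 6 DLT-evaluable patients).
- In 4.1.2, tie the statement that level 0 is intolerable to the rule of two or more DLTs in 9.1.1.
- If the sponsor intended a stricter zero-of-six gate when Level 1 was dropped, state that threshold in both 4.1.2 and 9.1.1, with the action to take after one DLT. The sponsor should choose, because the first option would loosen a deliberately strict gate if that was the intention. The price of the strict gate is a lower chance of releasing level 0: at an assumed 5% rate, 73.5% instead of 96.7%.
- Remove the Level 1 remnants: the escalation rule in 9.1.1, which now leads from level 0 to a level that no longer exists, and the cohort example in 9.2 that still counts patients at level 1.

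The cost is protocol wording only, and N stays at 24. Under the ≤ 1 of 6 option there is practically no delay at the stated accrual. Section 9.1.1 already pauses a full cohort until five of six are evaluated, and five evaluated without DLT already assure at most one in six.
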